10.6 Safety Analysis

The primary safety variable monitored will be the occurrence of adverse events. The severity of each adverse event observed will be evaluated as serious or not serious as defined by the MEEI HSC and the occurrence will be evaluated as expected or unexpected. The relationship of the event to the study medication will be assessed by the investigator as possibly, probably, or definitely related. Safety variables will be evaluated at screening and at all study visits. If adverse events occur, the first concern will be the safety of the study participants. Any serious adverse event occurring

during the study period will be immediately reported to MEEI IRB. Directed questioning (Ocular Tolerability and Compliance Questionnaire – Appendix I) and examination will then be done to assess tolerability. These questions are used to assess common and expected symptoms related to instillation or use of the study eye drops. Subjects will be asked to rate their symptoms from trace to severe.

Additional steps taken to assess safety will be followed as outlined in section 8.1 of this SUPP M form.

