8. SAFETY AND EFFECTIVENESS ASSESSMENTS

8.1 Safety Assessments

The primary safety variable monitored will be the occurrence of adverse events. The severity of each adverse event observed will be evaluated as serious or not serious and the occurrence will be evaluated as expected or unexpected. The relationship of the event to the study medication will be assessed by the investigator as possibly, probably, or definitely related. Safety variables will be evaluated at all study visits. If adverse events occur, the first concern will be the safety of the study participants. Any serious adverse event occurring during the study period will be immediately reported to MEEI IRB. At each visit throughout the study, the investigator will begin querying for adverse events by asking each subject a general, non-directed question such as "How have you been feeling since the last visit?" or "How have your eyes been since the last visit?"

The investigator will ask questions to subjects at each visit to determine if they have had any changes to the use of concomitant medications since the previous visit. A comprehensive eye examination including best-corrected visual acuity, measuring intraocular pressure, evaluation of the condition of conjunctiva, cornea, anterior chamber, iris/pupil, lens, vitreous, macula and optic nerve will be performed. Any changes in the study eyes from the screening visit will be recorded. If a subject contracts infectious conjunctivitis, they will be instructed to discard the remainder of the study drug and new drug will be sent from the host site pharmacy, Massachusetts Eye and Ear Infirmary.

If treatment with artificial tears is inadequate, or the subject develops severe form of ocular surface disease and dry eye, for the safety and proper treatment of the subject, the investigator can unmask the subject's treatment assignment to determine which

treatment has been assigned and institute appropriate follow-up care. However, the subject will be kept in the study so we can do the "intent-to-treat" analysis.

Withdrawal from the study will happen if any of the following occurs:

- Investigator determination that it is not in the best interest of the subject to continue participation.
- Subject's wish to withdraw for any reason.

After being withdrawn, subjects will be followed according to each case until the adverse event is resolved.

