9. ADVERSE EVENT RECORDING AND REPORTING

9.1 Recording Requirements

Research subjects will be routinely questioned about adverse events at study visits. All observed or volunteered adverse events (serious or non-serious) and abnormal test findings, regardless of study group or suspected causal relationship to the study drug(s) or device(s) will be recorded in the subjects' case histories (source data, case report form). For all adverse events, sufficient information will be pursued and/or obtained so as to permit 1) an adequate determination of the outcome of the event (i.e., whether the event should be classified as a serious adverse event) and; 2) an assessment of the causal relationship between the adverse event and the study drug(s) or device(s).

Adverse events or abnormal test findings thought to be associated with the study drug(s) or device(s) will be followed until the event (or its sequel) or the abnormal test finding resolves or stabilizes at a level acceptable to the Investigator.

An abnormal test finding will be classified as an adverse event if one or more of the following criteria are met:

- The test finding is accompanied by clinical symptoms
- The test finding necessitates additional diagnostic evaluation(s) or medical/surgical intervention; including significant additional concomitant drug treatment or other therapy
- The test finding leads to a change in study drug dosing or discontinuation of subject participation in the clinical research study
- The test finding is considered an adverse event by the Investigator. Note: simply repeating a test finding, in the absence of any of the other listed criteria, does not constitute an adverse event.

The Investigator will promptly review documented adverse events and abnormal test findings to determine 1) if the abnormal test finding should be classified as an adverse event; 2) if there is a reasonable possibility that the adverse event was caused by the study drug(s); and 3) if the adverse event meets the criteria for a serious adverse event.

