11. DATA AND SAFETY MONITORING

11.1 Data and Safety Monitoring Plan

The PI, research fellows, research coordinators, and technicians involved with this protocol will be required to read the protocol, participate in a group meeting to discuss roles before the protocol is approved, and participate in weekly clinical research meetings. The pharmacy and the clinical fellows on the protocol will be required to read the protocol and separate meetings will be created to discuss roles as they relate to the protocol.

A copy of the approved protocol and study related materials will be placed on a shared network drive accessible to authorized research staff involved in this study and on IRBnet.org.

The primary safety variable monitored will be the occurrence of adverse events. The severity of each adverse event observed will be evaluated as outlined in section 10.6 by the treating investigator. The PI will be made aware of all AEs within one week. The number of AEs related to increased pressure will be monitored and collated throughout the course of the study. Should the investigator need to be un-masked to treatment assignment to determine if there is a relationship with one of the study medications, treatment information will be provided by the MEEI Pharmacy.

The ocular surface exam and IVCM imaging will only be performed by a research technician, fellow, or investigator to ensure adherence to the required tests and accurate assessments.

The study coordinator will be responsible for monitoring each visit to ensure that the procedures are performed as outlined in the protocol and documented appropriately.

The images acquired will be checked for accuracy by the research fellows after acquisition and also during image analysis to ensure that the nasal conjunctiva has been imaged appropriately as laid out in the IRB-approved protocol.

Raw data collected for this study will be entered into a master database by the study coordinator, research technician, or fellow and uploaded for access to the principal investigator and all authorized research staff members on the U-Drive of password-protected computers located in the Cornea Research Department.

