14.2 Case Report Form(s)

Appendix I: Ocular Tolerability and Compliance Questionnaire

After you instill the study medication, how intensely have you experienced the following symptoms in each eye?

Itching

Right Eye: None Trace Mild Moderate Severe

Left Eye: None Trace Mild Moderate Severe

Burning Sensation

Right Eye: None Trace Mild Moderate Severe

Left Eye: None Trace Mild Moderate Severe

Foreign Body Sensation

Right Eye: None Trace Mild Moderate Severe

Left Eye: None Trace Mild Moderate Severe

Discharge

Right Eye: None Trace Mild Moderate Severe

Left Eye: None Trace Mild Moderate Severe

Redness

Right Eye: None Trace Mild Moderate Severe

Left Eye: None Trace Mild Moderate Severe

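### Adverse-event severity is defined as serious or not serious, so most non-serious events have no stated intensity grade

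*Combined protocol and SAP*

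**What the plan says.** Three sections of the combined protocol and SAP deal with adverse-event severity, and they agree.

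- Section 10.6 (Safety Analysis): "The severity of each adverse event observed will be evaluated as serious or not serious as defined by the MEEI HSC".
- Section 8.1 (Safety Assessments): "The severity of each adverse event observed will be evaluated as serious or not serious".
- Section 11.1 (Data and Safety Monitoring Plan): "The severity of each adverse event observed will be evaluated as outlined in section 10.6 by the treating investigator".

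Section 9.1 (Recording Requirements) asks for enough information to allow "an adequate determination of the outcome of the event (i.e., whether the event should be classified as a serious adverse event", together with a causality assessment. It does not ask for intensity.

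Section 10.6 also brings in the tolerability questionnaire of Appendix I: "Subjects will be asked to rate their symptoms from trace to severe". It sets the scope of that questionnaire: "These questions are used to assess common and expected symptoms related to instillation or use of the study eye drops". Sections 8.1, 10.6 and 11.1 all name adverse-event occurrence as the primary safety variable. Section 10.6 does not say how events or questionnaire ratings will be summarised or compared between arms.

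**The concern.** Seriousness and severity are different attributes of an event. Seriousness is a classification that drives reporting. Severity is how intense the event is. A severe event can be non-serious, and the plan's two-level variable places it in the same class as a trivial one.

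The plan uses the word in its ordinary sense elsewhere. Section 5.4 has an investigator judge how severe an infectious conjunctivitis is before deciding whether the subject remains eligible. The adverse-event scale in 8.1 and 10.6 has no value in which to record that judgement.

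At stake is the description of tolerability and harm for a six-week steroid taper against an artificial tear. If few or no events are serious, the recorded severity cannot show whether one arm's events were worse than the other's. Intensity that is not recorded at the time is hard to reconstruct reliably later.

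**Working it through.** **Step 1: what carries an intensity measure.** The plan states no figure on this point that could be reproduced, so the check begins by setting the passages side by side.

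| Safety information | Where | Scale stated |
|---|---|---|
| Any adverse event | 8.1, 10.6; 11.1 by reference | 2 levels: serious, not serious |
| Itching, burning, foreign body sensation, discharge, redness | Appendix I | 5 levels, each eye: "Right Eye: None Trace Mild Moderate Severe" (same for the left eye) |
| Any other symptom after instillation | Appendix I, continued | yes/no and free text |
| IOP | 7.8 (Table 1), 10.2 | numeric, at screening, week 2 and week 6 |
| Visual acuity | 7.8 (Table 1) | measured at the same three visits |
| Pressure-related adverse events | 11.1 | number of events; no grade |
| Infectious conjunctivitis | 5.4 | severity to be assessed; no scale given |

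No section gives a mild/moderate/severe grade, or an equivalent, for adverse events in general. The events left without one are those outside the five questionnaire symptoms and the measured variables. The questionnaire ratings come from the subject, and nothing ties them to the adverse-event record.

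**Step 2: when the substitutes may be absent.** Section 7.6 requires only an adverse-event review when a subject attends for a visit unrelated to the study. Section 7.7 adds no procedures at early termination, although 8.1 and 9.3 follow withdrawn subjects until the event resolves. In these situations the adverse-event record may be the only study safety information, and its stated severity has two levels.

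**Step 3: how likely the two-level variable is to be constant.** Inputs:

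- n = 50 subjects (sections 3.1 and 10.3).
- p = probability that a subject has at least one serious event. The documents give no value, so 0.5% to 2% is assumed for illustration, equal in both arms and independent between subjects.

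Formula: P(no serious event in the trial) = (1 − p)^n.

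- p = 0.5%: 0.995^50 = 0.778, or 78%.
- p = 2%: 0.98^50 = 0.364, or 36%.

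In that case every recorded event in both arms has the value not serious. The calculation describes the severity variable alone. It does not measure how many events would be misjudged or how large a difference would be hidden.

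**The case against.** The strongest reply is that the plan collects much more than this one variable.

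- IOP, the steroid effect that the protocol itself singles out, is measured numerically at three visits. Section 11.1 tracks pressure-related events separately, and section 13.2 uses a numeric IOP threshold. For pressure, a measurement in every subject is more informative than a three-level grade.
- Appendix I grades five common drop-related symptoms in each eye.
- Acuity, slit-lamp examination, funduscopy and staining are repeated at follow-up visits, and 8.1 records changes from screening.
- Section 9.1 considers whether an abnormal finding needed intervention, changed dosing or ended participation, which says something about its consequence.
- The primary safety variable is occurrence. The plan nowhere makes the serious/not-serious split the comparison between arms.
- The hospital committee's definitions and any separate adverse-event form are not in the documents, so an intensity field there cannot be ruled out.

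All of this stands, and it limits the point. A reader might infer that the safety analysis cannot separate mild from severe events at all, or that the arms would look alike even if one had clearly worse events. The documents support neither reading: counts, expectedness, relatedness, IOP, acuity and Appendix I ratings can all differ between arms without a single serious event.

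The reply does not remove the gap. The criteria in 9.1 decide whether a test finding counts as an adverse event; they do not grade it. And if an unseen form does hold an intensity field, 8.1 and 10.6 would still define severity as seriousness and would need correcting.

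**Conclusion.** The point holds in a limited form. Sections 8.1 and 10.6, and 11.1 by reference, state a rule that puts seriousness in the place of severity. Followed as written, it leaves non-serious adverse events without a stated intensity grade, except for the five Appendix I symptoms and what is captured by measured variables such as IOP and visual acuity.

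The size is a 36% to 78% chance that the severity variable does not vary at all. This rests on the assumed 0.5% to 2% risk, a common risk in both arms, independence between subjects and exactly 50 subjects. Section 5.2 allows withdrawn subjects to be replaced, so more than 50 might be exposed, which would lower these probabilities somewhat.

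The effect is confined to safety reporting. The primary endpoints, the sample size and the study discontinuation criterion are unaffected.

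**What to change.** In sections 8.1 and 10.6 and on the adverse-event CRF, record two separate items for every event: seriousness (serious or not serious, by the committee's definition) and severity (mild, moderate or severe). Section 11.1 then follows through its reference to 10.6.

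In 10.6, add a table giving, for each arm, the number of subjects with any event by maximum severity. Use the safety population of section 10.5, which groups subjects by treatment received. It would also help to state there how the Appendix I ratings and IOP will be summarised by arm, since those data are already collected.

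The cost is one extra CRF field, one extra table and the change in wording. No visit, procedure or treatment rule changes. If the form already has an intensity field, only the protocol text and the table are needed.

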10.7 Interim Analysis

N/A

11. DATA AND SAFETY MONITORING

11.1 Data and Safety Monitoring Plan

The PI, research fellows, research coordinators, and technicians involved with this protocol will be required to read the protocol, participate in a group meeting to discuss roles before the protocol is approved, and participate in weekly clinical research meetings. The pharmacy and the clinical fellows on the protocol will be required to read the protocol and separate meetings will be created to discuss roles as they relate to the protocol.

A copy of the approved protocol and study related materials will be placed on a shared network drive accessible to authorized research staff involved in this study and on IRBnet.org.

The primary safety variable monitored will be the occurrence of adverse events. The severity of each adverse event observed will be evaluated as outlined in section 10.6 by the treating investigator. The PI will be made aware of all AEs within one week. The number of AEs related to increased pressure will be monitored and collated throughout the course of the study. Should the investigator need to be un-masked to treatment assignment to determine if there is a relationship with one of the study medications, treatment information will be provided by the MEEI Pharmacy.

The ocular surface exam and IVCM imaging will only be performed by a research technician, fellow, or investigator to ensure adherence to the required tests and accurate assessments.

The study coordinator will be responsible for monitoring each visit to ensure that the procedures are performed as outlined in the protocol and documented appropriately.

The images acquired will be checked for accuracy by the research fellows after acquisition and also during image analysis to ensure that the nasal conjunctiva has been imaged appropriately as laid out in the IRB-approved protocol.

Raw data collected for this study will be entered into a master database by the study coordinator, research technician, or fellow and uploaded for access to the principal investigator and all authorized research staff members on the U-Drive of password-protected computers located in the Cornea Research Department.

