3.2.2 Masking Procedures

The study drugs will be labeled by the Massachusetts Eye & Ear pharmacy with instructions for storage, the name of the study, an expiration date, and a notice that

the bottle may contain Lotemax. The pharmacy will maintain a master list of the participants' name, unique identifier, and the coded treatment assignment. The randomization scheme and treatment assignment will be held in the pharmacy to ensure that the investigator and study team remain masked. Participants, investigators, image analysts, and the sponsor (GSK) will be masked to the treatment group.

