3.2.3 Breaking the Mask

A subject's medication may be unmasked at any point for a medical emergency or to supplement a serious adverse event (SAE) report. The subjects will be unmasked at the end of the study in order to provide optimal ongoing care.

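### Section 11.1 lets the code be opened so that the investigator can judge relatedness, a ground not named in 3.2.3; a rating made that way is unmasked and can be biased

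*Combined protocol and SAP*

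**What the plan says.** Section 3.2.2 makes the masking commitment: "Participants, investigators, image analysts, and the sponsor (GSK) will be masked to the treatment group". Section 3.2.3 then says when the mask can be broken during the study: "A subject's medication may be unmasked at any point for a medical emergency or to supplement a serious adverse event (SAE) report". Unmasking everyone at the end of the study is a separate provision there.

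Section 11.1, on adverse-event monitoring, describes another use of the code: "Should the investigator need to be un-masked to treatment assignment to determine if there is a relationship with one of the study medications", in which case the pharmacy supplies the assignment. Sections 5.5 and 8.1 let the investigator unmask when artificial-tear treatment is inadequate or severe ocular surface disease develops, and keep the subject in the study for the intention-to-treat analysis.

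On the rating itself, section 10.6 says: "The relationship of the event to the study medication will be assessed by the investigator as possibly, probably, or definitely related".

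No section requires the rating to be recorded before the code is opened, or a masked examiner to take over afterwards. Section 10.5 does not say how grades taken after unmasking are handled. Section 12.1 keeps dispensing and randomization logs in the pharmacy but mentions no record of code breaks.

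**The concern.** Relatedness is a judgement. A rater who knows the arm can be expected to call events typical of a steroid, raised pressure above all, related more readily on Lotemax and less readily on the artificial tear. The rating has uses: it is listed in the safety analysis (10.6), and whether an SAE goes to the FDA depends on it (9.2).

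There is a second possible consequence. Once an investigator knows a subject's arm, any sign that the same person grades later for that subject is no longer a masked observation, and several secondary efficacy endpoints are graded at the slit lamp.

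**Working it through.** No formula or stated figure is involved, so the check sets the sections side by side.

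**1. Grounds for unmasking during the study**

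| Section | Ground | Limited to emergencies or serious events? |
|---|---|---|
| 3.2.3 | Medical emergency; supplementing an SAE report | Yes |
| 5.5 and 8.1 | Inadequate artificial-tear treatment; severe ocular surface disease | No, tied to the state of the disease |
| 11.1 | Investigator's need to decide drug relationship | No limit stated, and no criterion for need |

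The lists differ, and no section says which one governs.

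**2. Scope of 11.1.** The same paragraph says "The PI will be made aware of all AEs within one week" and then turns to collating pressure-related events, before the sentence on unmasking. Section 9.1 asks for a causality assessment of all adverse events. Nothing in the text keeps the 11.1 route away from non-serious events. Since 3.2.3 already covers SAE reports, what 11.1 can add is mainly non-serious events.

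**3. The relatedness rating.** The rater under 10.6 is the investigator. The person who receives the code under 11.1 is the investigator. The purpose of opening it is to make the rating. Whenever the route is used as written, the code comes first and the rating second, so the rating is unmasked by construction.

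**4. Later grading.** Section 11.1 also says: "The ocular surface exam and IVCM imaging will only be performed by a research technician, fellow, or investigator". Bias in a sign needs three things together: a code break, a scheduled exam still to come, and a grader who knows the assignment. Follow-up visits are at Week 2 (± 3 days) and Week 6 (± 1 week), so this concerns mainly events raised by the Week 2 visit. The documents permit the combination but do not make it certain, because a technician or fellow may do the exam.

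**5. Which endpoints are exposed.** Section 10.2 lists seven secondary measures. Five are taken by clinic staff (corneal staining, conjunctival staining, TBUT, Schirmer, IOP) and two are questionnaires (5 + 2 = 7). Staining scores (0–3 per region, Appendix IV) and TBUT, judged by eye, are the most open to the observer. Schirmer is a length marked on a strip at five minutes and IOP is a tonometer reading, so both are less so. The primary endpoints (10.1) are all IVCM, with analysts masked under 3.2.2. The protection is large but not complete, because 11.1 lets an investigator acquire the images.

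**6. Size.** For a sign, the bias in the mean difference would be p_L × δ_L − p_A × δ_A. Here p is the proportion of an arm graded by someone who knows the assignment, and δ is the mean grading shift in those subjects (L for Lotemax, A for artificial tear). The documents give none of the four terms and no expected adverse-event rate. The number of events that would be rated after a code break is equally unknown. There is nothing to compute.

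**The case against.** The strongest reply is that 11.1 is conditional and its main clause only says who supplies the code. Its phrase about a relationship with a study medication is close to 9.2, where a related SAE goes to the FDA. On that reading, 11.1 is merely the mechanism for the SAE ground in 3.2.3. This reading is possible. A reader might infer that 11.1 opens the mask for every adverse event in breach of a closed list, but the documents do not go that far: 11.1 does not say *any* event, and 3.2.3 does not say *only*. What remains is that the text does not limit 11.1 to serious events. Even on the narrow reading, an SAE's relatedness would be rated with the arm known.

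A reader might also infer that later slit-lamp grades will be biased because the same team does them. That is not established; it depends on who grades and whether a visit remains.

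The consequence for safety is also bounded. The primary safety variable is the occurrence of adverse events, which does not depend on relatedness, and no between-arm comparison of related events is planned. Section 9.1 classes causality that is unknown and questionable as drug-associated for reporting, which partly limits downgrading in either arm. These points stand and keep the matter modest. They do not make an unmasked rating a masked one.

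Finally, 5.1 has a procedure for raised pressure attributed to Lotemax, so there may be a clinical reason to know the arm. That is a reason not to forbid the code break. It does not prevent recording a masked rating first.

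**Conclusion.** The point holds. Sections 3.2.3, 5.5, 8.1 and 11.1 give different grounds for unmasking. A relatedness rating made by the 11.1 route is made knowing the arm and can be biased. That part is direct and needs only that the sentence be followed as written. Bias in the observer-graded secondary signs is conditional on an unmasked investigator doing a later exam. The primary endpoints are largely out of reach.

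The size cannot be stated. A reader might multiply an assumed share unmasked by an assumed grading shift to get a figure in standard deviations, but neither input is in the documents, and a single shift would not suit measures as unlike as staining and Schirmer. A reader might also conclude that code breaks should be confined to the grounds in 3.2.3. The documents do not support that either: they contain several conflicting rules and do not rank them.

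The change is worth making because it is specific, cheap and removes the direct route to bias.

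**What to change.** - **Order of rating.** Amend 11.1 so that the investigator records relatedness while masked, before any code is opened. Keep that rating for the safety analysis, and record any opinion formed after unmasking separately.
- **Log.** Record each code break with date, reason and who was told.
- **Analysis.** Keep intention-to-treat as primary. Add a supportive sensitivity analysis of the observer-graded signs that excludes values graded after unmasking. State that it conditions on a post-randomisation event, much the same caution that 10.5 gives for not planning a per-protocol analysis.
- **Reconcile.** Bring the grounds in 3.2.3, 5.5, 8.1 and 11.1 into one consistent statement. Which grounds apply, and how such subjects are managed, is for the sponsor and clinicians.

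The cost is protocol wording, a short log and one extra table. The small downside is that some masked ratings will be less certain; 9.1 already says how uncertain causality is classified for reporting. Nothing here delays or restricts emergency unmasking: if the code has to be opened before a rating can be written down, the log should say so.
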